11 PROTOCOL AMENDMENT HISTORY

Version	Brief Description and Rationale
1	Initial Version of this document

Document: TDOC-0054657 Version: 1.0; CURRENT; Most-Recent; Effective

Status: Effective

Short Title:

Statistical Analysis Plan CLE383-C004

Full Title:

Statistical Analysis Plan CLE383-C004 / NCT03349632

Protocol Title: Clinical Comparison of 4 Daily Disposable Soft Contact

Lenses

Project Number: CLE383-C004

Protocol TDOC Number: TDOC-0054506

Author:

Template Version: Version 4.0

Approvals: See last page for electronic approvals

Job Notes:

This is the original (Version 1.0) Statistical Analysis Plan for this study. This version of the Statistical Analysis Plan is based on Version 1.0 of the study protocol.

Document: TDOC-0054657 Version: 1.0; CURRENT; Most-Recent; Effective

Status: Effective

Executive Summary:

Key Objective:

The primary objective of this study is to evaluate the overall performance of Daily Disposable (DD) T2 Soft Contact Lenses when compared to ACUVUE OASYS® Brand Contact Lenses 1-Day with HydraLuxeTM Technology (Oasys 1-Day), CooperVision® MyDay® (MyDay) and 1-Day ACUVUE® MOIST (Moist) lenses.

Decision Criteria for Study Success:

Decision criteria for study success are not applicable for this study.

 ${\bf Alcon \textbf{-} Business} \ Use \ Only \ {\tt Statistical} \ {\tt Analysis} \ {\tt Plan}$

Version: 1.0; CURRENT; Most-Recent; Effective

Effective Date: 17-Nov-2017

Status: Effective

Document: TDOC-0054657

Table of Contents

Statistic	al Analysis Plan CLE383-C004	1
Table of	f Contents	3
List of T	Tables	4
1	Study Objectives and Design	5
1.1	Study Objectives	5
1.2	Study Description	
1.3	Randomization	
1.4	Masking	6
1.5	Interim Analysis	6
2	Analysis Sets	6
2.1	Safety Analysis Set	6
		6
4	Effectiveness Analysis Strategy	
4.1	Effectiveness Endpoints	7
4.2	Effectiveness Hypotheses	8
4.3	Statistical Methods for Effectiveness Analyses	8
4.3.1	Primary Effectiveness Analyses	8
		9
4.4	Multiplicity Strategy	9
4.5	Subgroup Analyses and Effect of Baseline Factors	9
4.6	Interim Analysis for Effectiveness	9
5	Safety Analysis Strategy	9
5.1	Safety Endpoints	9
5.2	Safety Hypotheses	10
5.3	Statistical Methods for Safety Analyses	10
5.3.1	Adverse Events	10
5.3.2	Biomicroscopy Findings/Slit Lamp Examination	
5.3.3	Device Deficiencies	11
6	Analysis Strategy for Other Endpoints	11
I		11

Alcon - Bu	siness Use Only Statistical Analysis Plan	Effective Date: 17-Nov-2017
Document: T Status: Effect	Version: 1.0; CURRENT; Most-Recent;	Effective
8	References	11
9	Revision History	11
10	Appendix	12
	List of Tables	

1.1 Study Objectives

PRIMARY OBJECTIVE

The primary objective of this study is to evaluate the overall performance of DD T2 lenses when compared to Oasys 1-Day, MyDay and Moist lenses.

1.2 Study Description

Key components of the study are summarized in Table 1-1.

Table 1-1 Study Description Summary

G: 1 D :			
Study Design	Prospective, randomized, parallel group, bilateral crossover,		
	double-masked		
Study Population	Volunteer subjects aged 18 or over who are soft daily disposable		
	contact lens wearers (excluding current Oasys 1-Day, MyDay and		
	Moist wearers), have at least 3 months of contact lens wearing		
	experience, and who wear their habitual lenses at least 5 days per		
	week and at least 8 hours per day.		
	Target to complete: 60 (20 per each parallel group)		
	Planned to enroll: ~66 (~22 per each parallel group)		
Number of Sites	~3 (US)		
Test Product Daily Disposable T2 Soft Contact Lenses (DD T2)			
Control Products	ACUVUE OASYS® Brand Contact Lenses 1-Day with		
	HydraLuxe™ Technology (Oasys 1-Day)		
	CooperVision® MyDay® (MyDay)		
	• 1-Day ACUVUE® MOIST (Moist)		
Duration of Treatment	~20 days total duration		
	• Test Product: 8 days (-1/+2 days)		
	Control Products: 8 days (-1/2 days)		
Visits	Visit 1, Day 1: Baseline/Dispense Lens 1		
	Visit 2, Week 1 [Day 8 (-1/+2 Days)]: Follow-up Lens 1/Dispense		
	Lens 2		
	Visit 3, Week 2 [Day 8 (-1/+ 2 Days)]: Follow-up Lens 2/Exit		

Document: TDOC-0054657 Version: 1.0; CURRENT; Most-Recent; Effective

Status: Effective

1.3 Randomization

A member of the Randomization Programming group at Alcon who is not part of the study team will generate the randomized allocation schedule(s) for study lens sequence assignment. Randomization will be implemented in iMedidata Balance.

Qualifying subjects will be randomized in a 1:1:1:1:1 manner to one of 6 lens sequences consisting of the test lens and a control lens as described below. For each sequence, subjects wear 1st lens then crossover to 2nd lens.

Sequence 1: DD T2/Oasys 1-Day

Sequence 2: Oasys 1-Day/DD T2

Sequence 3: DD T2/MyDay

Sequence 4: MyDay/DD T2

Sequence 5: DD T2/Moist Sequence 6: Moist/DD T2

1.4 Masking

This study is double-masked.

1.5 Interim Analysis

There are no plans to conduct an interim analysis and no criteria by which the study would be terminated early based upon statistical determination

2 Analysis Sets

2.1 Safety Analysis Set

[figure not shown]
Safety analyses will be conducted using the safety analysis set on a treatment-emergent basis. As such, the safety analysis set will include all subjects/eyes exposed to any study lenses evaluated in this study. For treatment-emergent safety analyses, subjects/eyes will be categorized under the actual study lens exposed in the corresponding lens sequence.

Adverse events occurring from the time of informed consent but prior to first exposure to study lenses will be summarized in subject listings.

Document: TDOC-0054657 Version: 1.0; CURRENT; Most-Recent; Effective

Status: Effective

4 Effectiveness Analysis Strategy

This study defines one primary endpoint Data for DD T2 will be summarized according to the crossover control worn per each parallel group. The Safety Analysis Set will serve as the primary set for all effectiveness analyses.

Continuous variables will be summarized using the number of observations, mean, standard deviation, median, minimum, and maximum. Categorical variables will be summarized with counts and percentages from each category.

All data obtained in evaluable subjects/eyes will be included in the analysis. No imputation for missing values will be carried out for the primary analysis.

A listing of selected effectiveness data will also be provided.

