5.2 Unscheduled Visits

Any visit that occurs between regularly scheduled visits is an Unscheduled Visit. If a subject requires an Unscheduled Visit, he/she must be advised to return to the office wearing the study lenses, if at all possible (unless he/she is experiencing a sign or symptom [as indicated in Section 3.3 Risks and Benefits]). During all unscheduled visits, the Investigator must conduct the following procedures:

- Collect AE and device deficiency information
- Assess and record changes in medical condition or concomitant medication
- Assess and record VAs
- Perform biomicroscopy (assessments with or without lenses, as possible)

In addition, all procedures for Visit 3 (Follow-up Lens 2/Exit) should be completed (as possible). The Investigator may perform additional procedures for proper diagnosis and treatment of the subject. The Investigator must document this information in the subject's case history source documents.

If during an Unscheduled Visit the subject is discontinuing the study lenses or discontinuing from the study, the Investigator must conduct Exit procedures according to Table 1-1: Schedule of Study Procedures and Assessments, as possible.

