5.3 Discontinued Subjects

Discontinued subjects are those who withdraw or are withdrawn from the study after signing the informed consent, including screen failures. Subjects may discontinue from the study at any time for any reason. Subjects may also be discontinued from the study at any time if, in the opinion of the Investigator, their continued participation poses a risk to their health. Discontinued subjects will not be replaced (ie, their subject numbers will not be re-assigned/re-used).

Should a subject exhibit any clinically relevant signs, symptoms, or other clinical observations that possibly could be associated with suspected sensitivity or intolerance to one of the study treatments, the Investigator must document those observations on an AE Form.

Any subject who exits early from the study (excluding screen failures) must undergo all procedures outlined at Visit 3, as applicable.

Document: TDOC-0054506 Version: 1.0; CURRENT; Most-Recent; Effective

Status: Effective Page 22 of 38

The Investigator must document the reason for study or treatment discontinuation in the subject's case history source documents.

To ensure the safety of all subjects who discontinue early, Investigators must assess each subject and, if necessary, advise them of any therapies and/or medical procedures that may be needed to maintain their health.

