6.1 Subject Evaluability

The final subject evaluability will be determined prior to breaking the code for masked treatment sequence assignment and locking the database, based on the Deviations and Evaluability Plan.

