6.2 Analysis Data Sets

6.2.1 Safety Analysis Set

Safety analyses will be conducted using the safety analysis set on a treatment-emergent basis. As such, the safety analysis set will include all subjects/eyes exposed to any study lenses evaluated in this study. For treatment-emergent safety analyses, subjects/eyes will be categorized under the actual study lenses exposed.

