4.1 Effectiveness Endpoints

Primary Endpoint

The primary endpoint is the subjective rating on overall quality of vision, collected binocularly on a scale of 1 (Poor) to 10 (Excellent).

Secondary Endpoint

No secondary endpoint is defined for this study.

[figure not shown]

Alcon - Business Use Only Statistical Analysis Plan

Document: TDOC-0054657 Version: 1.0; CURRENT; Most-Recent; Effective

Effective Date: 17-Nov-2017

Status: Effective

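### Do the wording on evaluable subjects and the unscheduled ratings leave the primary vision-rating summary undefined?

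*SAP*

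**What the plan says.** **Analysis set.** SAP Section 4 and Protocol 6.4 both state: "The Safety Analysis Set will serve as the primary set for all effectiveness analyses". Protocol 6.2.1 defines its membership: "the safety analysis set will include all subjects/eyes exposed to any study lenses evaluated in this study". SAP 2.1 defines it the same way.

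**Data included.** SAP Section 4 then says: "All data obtained in evaluable subjects/eyes will be included in the analysis". The next sentence rules out imputation for the primary analysis. The protocol has the same pair of sentences in 6.6, under the heading on missing data.

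**Evaluability.** Protocol 6.1 says: "The final subject evaluability will be determined prior to breaking the code for masked treatment sequence assignment and locking the database", and that this is done "based on the Deviations and Evaluability Plan". That plan is a separate document. Neither the protocol nor the SAP gives its criteria in the visible text.

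**Endpoint and timing.** The primary endpoint (Protocol 6.4.1, SAP 4.1) is a binocular rating of overall quality of vision from 1 to 10, with no visit named. The schedules (Protocol Table 1-1 and the SAP appendix) mark it at Visit 2, labelled as follow-up of Lens 1, at Visit 3, the follow-up of Lens 2, and at unscheduled visits. Protocol 5.2 asks for the Visit 3 procedures at unscheduled visits as far as possible. On early exit, Protocol 5.3 says: "Any subject who exits early from the study (excluding screen failures) must undergo all procedures outlined at Visit 3, as applicable".

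**Use of the results.** The analysis is descriptive. There are no hypotheses (Protocol 6.4.1.1, SAP 4.2), and the SAP executive summary says success criteria do not apply.

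**The concern.** Exposed and evaluable are not the same thing. A subject who wore a lens but was later judged non-evaluable belongs to the Safety Analysis Set, yet is not covered by the sentence on included data. A programmer could ask which governs.

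The second worry is repeated ratings. If all data obtained were taken literally, a subject who came in early with a problem would give two ratings for one lens. Protocol 3.3 tells subjects to return promptly for symptoms that include vision changes, so the extra ratings could well be low ones. A subject who leaves during Lens 1 also completes the procedures of a visit labelled for Lens 2.

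The printed means and percentages are the whole effectiveness result, and each rests on about 20 ratings. One or two subjects could therefore move a mean noticeably, and the two alternative readings move it in opposite directions.

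**Working it through.** **1. The plan's own figures.** Both documents give 60 subjects to complete (20 per group) and about 66 to enroll (about 22 per group). 3 × 20 = 60 and 3 × 22 = 66, an allowance of 1 − 60/66 = 9.1% for attrition. So 20 to 22 ratings per lens within a parallel group is the right scale.

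**2. How much the readings could differ.** The documents contain no ratings, so these inputs are assumptions:

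- n = 20 to 22 subjects per lens and group
- k = 1 or 2 dissatisfied subjects
- x = 1 to 5, the rating those subjects give
- m = 8 to 9, the mean of the other subjects

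The three readings give:

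- A, all exposed, one rating per subject: [(n − k)m + kx] / n
- B, as A plus one unscheduled rating from each dissatisfied subject: [(n − k)m + 2kx] / (n + k)
- C, evaluable subjects only, if exactly the dissatisfied ones are excluded: m

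With n = 22, k = 2, x = 3 and m = 8.5:

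- A = (20 × 8.5 + 2 × 3) / 22 = 176/22 = 8.00
- B = (20 × 8.5 + 4 × 3) / 24 = 182/24 = 7.58
- C = 8.50

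The percentage in the 3–4 category would be 2/22 = 9.1%, 4/24 = 16.7% and 0/20 = 0%.

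Over the whole assumed range:

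| | k = 1 | k = 2 |
|---|---|---|
| B minus A | −0.12 to −0.36 | −0.23 to −0.65 |
| C minus A | +0.14 to +0.40 | +0.27 to +0.80 |

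With no unscheduled ratings B equals A. With every exposed subject evaluable C equals A.

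**3. Which reading the text supports.**

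- *Reading C* needs the word only, which the documents do not contain. They say that data from evaluable subjects are included; they do not say that other members of the named set are excluded. Placed next to the no-imputation rule, the sentence most naturally means that observed data are used as they stand.
- *Reading B* needs a rule that unscheduled ratings enter the primary summary. None is stated. Collecting a rating at an unscheduled visit does not make it part of the endpoint summary, and the schedule gives each lens one planned follow-up.
- *Reading A* needs only the named set and the visit schedule.

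**4. Early exit.** The Visit 3 procedures apply only as applicable, and the schedule describes the rating as one made with the study lenses. A subject who leaves during Lens 1 has worn only Lens 1, so the rating belongs to Lens 1. Nothing assigns it to Lens 2.

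**The case for a change.** The best case for a change is that evaluability must do some work, since Protocol 6.1 sets up a formal determination of it, and neither document links it to the Safety Analysis Set. The tick for the rating at unscheduled visits is unbracketed, while the visual acuity rows are bracketed as performed when necessary. The summaries count observations, not subjects. The SAP does give such rules for safety: a baseline visit (5.3), adverse events assigned to a lens by onset (5.3.1), and biomicroscopy tabulated by visit (5.3.2). In a descriptive study the printed means are the result, and a clarification would take two sentences.

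Much of this stands as description. The link between evaluability and the analysis set is unstated, and no visible text fixes the visit.

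The step to a biased comparison does not stand. Evaluability is settled before unmasking and database lock, and its criteria are not visible, so a tie between exclusion and lens performance is conjecture. Extra low ratings are possible but not assured. Symptomatic subjects are advised to remove their lenses (Protocol 3.3), and they are exempt from the advice to return wearing them (Protocol 5.2), so a rating with the study lenses may not always be obtained.

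The visible copy is also incomplete. SAP Section 3 and text around the endpoint are missing, so a visit rule there cannot be ruled out, and its absence from these pages does not count as an omission.

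**Conclusion.** This is a gap that analysts fill sensibly. The wording is ambiguous, but it neither contradicts itself nor instructs anyone to pool every rating. Following the named set and the schedule leads to one Day 8 rating per subject and lens in all exposed subjects, with an early-exit rating credited to the lens worn.

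The possible shifts, 0.12 to 0.65 points downward from double counting and 0.14 to 0.80 upward from exclusion, rest entirely on assumed ratings and on one or two affected subjects per lens. They also require a reading that the text does not state. With no hypotheses, no inference and no success criterion, no decision in the plan turns on them. A clarification would write down the default without correcting any stated rule shown to give a wrong result, so no change is called for.

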4.1 Effectiveness Endpoints

Primary Endpoint

The primary endpoint is the subjective rating on overall quality of vision, collected binocularly on a scale of 1 (Poor) to 10 (Excellent).

Secondary Endpoint

No secondary endpoint is defined for this study.

[figure not shown]

Alcon - Business Use Only Statistical Analysis Plan

Document: TDOC-0054657 Version: 1.0; CURRENT; Most-Recent; Effective

Effective Date: 17-Nov-2017

Status: Effective

4.2 Effectiveness Hypotheses

Primary Effectiveness

No inferences are to be made on the primary effectiveness endpoint, therefore no hypotheses are formulated.

4.3 Statistical Methods for Effectiveness Analyses

4.3.1 Primary Effectiveness Analyses

Descriptive statistics for continuous variables will be provided. Additionally, counts and percentages will be provided for the following categories: 9-10, 7-8, 5-6, 3-4, 1-2.

Document: TDOC-0054657 Version: 1.0; CURRENT; Most-Recent; Effective

Status: Effective

4.4 Multiplicity Strategy

No multiplicity adjustment needs to be considered for the effectiveness endpoints since no formal hypothesis testing will be conducted.

4.5 Subgroup Analyses and Effect of Baseline Factors

It is not expected that demographic or baseline characteristics will have an impact on the study results in this study. No subgroup analyses are planned.

4.6 Interim Analysis for Effectiveness

No interim analysis is planned for effectiveness endpoints.

5 Safety Analysis Strategy

5.1 Safety Endpoints

The safety endpoints are

- Adverse events (AE)
- Biomicroscopy Findings/Slit Lamp Examinations
 - Limbal hyperemia
 - o Bulbar hyperemia
 - Corneal staining
 - Conjunctival staining
 - Palpebral conjunctival observations
 - o Corneal epithelial edema
 - Corneal stromal edema
 - o Corneal vascularization
 - Conjunctival compression/indention
 - Chemosis
 - Corneal infiltrates
 - Other findings
- Device deficiencies

Document: TDOC-0054657 Version: 1.0; CURRENT; Most-Recent; Effective

Status: Effective

5.2 Safety Hypotheses

There are no formal safety hypotheses in this study. The focus of the safety analysis will be a comprehensive descriptive assessment of safety endpoints listed in Section 5.1.

5.3 Statistical Methods for Safety Analyses

The analysis set for all safety analyses is the safety analysis set as defined in Section 2.1. Baseline will be defined as the last measurement prior to exposure to study lenses on Visit 1. Safety variables will be summarized descriptively.

5.3.1 Adverse Events

The applicable definition of an AE is in the study protocol. All AEs occurring from when a subject signs informed consent to when a subject exits the study will be accounted for in the reporting.

Analysis and presentation of pre-treatment AEs will be separated from treatment-emergent AEs occurring during the study period. A pre-treatment AE is an event that occurs after signing informed consent but prior to exposure to study lenses. The period for treatment-emergent AE analysis starts from exposure to study lenses until the subject completes or is discontinued from the study. Each AE will be summarized under the exposed lens based upon the event onset date/time, up until the start of the next lens in the crossover sequence.

The following tables and supportive listings will be provided:

- Incidence of All Ocular Treatment-Emergent Adverse Device Effects
- Incidence of All Ocular Treatment-Emergent Adverse Events, Not Related
- Incidence of All Ocular Treatment-Emergent Adverse Events, Overall
- Incidence of All Nonocular Treatment-Emergent Adverse Device Effects
- Incidence of All Nonocular Treatment-Emergent Adverse Events, Not Related
- Incidence of All Nonocular Treatment-Emergent Adverse Events, Overall
- Listing of All Ocular Treatment-Emergent Adverse Events
- Listing of All Nonocular Treatment-Emergent Adverse Events
- Listing of All Ocular Pre-Treatment Adverse Events
- Listing of All Nonocular Pre-Treatment Adverse Events

5.3.2 Biomicroscopy Findings/Slit Lamp Examination

The following tables and supportive listings will be provided:

Document: TDOC-0054657 Version: 1.0; CURRENT; Most-Recent; Effective

Status: Effective

- Frequency and Percentage for Biomicroscopy Findings by Visit
- Incidence of Increased Severity by 2 or More Grades in Biomicroscopy Findings
- Listing of Subjects With Other Biomicroscopy Findings
- Listing of Subjects With Increased Severity by 1 Grade in Biomicroscopy Findings
 [This listing will include all relevant visit within the crossover period]
- Listing of Subjects With Increased Severity by 2 or More Grades in Biomicroscopy Findings [This listing will include all relevant visits within the crossover period]
- Listings of Subjects with Infiltrates

5.3.3 Device Deficiencies

The following tables and supportive listings will be provided:

- Frequency of Treatment-Emergent Device Deficiencies
- Listing of Treatment-Emergent Device Deficiencies
- Listing of Device Deficiencies Prior To Treatment Exposure

6 Analysis Strategy for Other Endpoints

Not applicable.

8 References

Not applicable.

9 Revision History

This is the original (Version 1.0) Statistical Analysis Plan for this study. This version of the Statistical Analysis Plan is based on Version 1.0 of the study protocol.

Document: TDOC-0054657 Version: 1.0; CURRENT; Most-Recent; Effective

Status: Effective

10 Appendix

Table 100-1 Schedule of Study Procedures and Assessments

Procedure/ Assessment	Visit 1, Day 1: Baseline/ Dispense Lens 1	Visit 2, Week 1: Day 8 of lens wear (-1/+2 days) Follow-up Lens 1/ Dispense Lens 2	Visit 3, Week 2: Day 8 of lens wear (-1/+2 days) Follow-up Lens 2/ Exit	Unscheduled Visit
Informed Consent	✓	-	-	-
Demographics	✓	-	-	-
Medical History	✓	-	-	-
Concomitant Medications	✓	(✓)	(✓)	(✓)
Inclusion/ Exclusion	✓	-	-	-
Habitual lens (brand, power)*	✓	-	-	-
VA w/ habitual correction (OD, OS, Snellen distance)*	✓	-	✓	(*)
Biomicroscopy	✓	✓	✓	✓
Dispense study lenses	✓	✓	-	-
VA w/ study lenses (OD, OS, Snellen distance)	✓	✓	✓	(✓)

Document: TDOC-0054657 Version: 1.0; CURRENT; Most-Recent; Effective

Status: Effective

Procedure/ Assessment	Visit 1, Day 1: Baseline/ Dispense Lens 1	Visit 2, Week 1: Day 8 of lens wear (-1/+2 days) Follow-up Lens 1/ Dispense Lens 2	Visit 3, Week 2: Day 8 of lens wear (-1/+2 days) Follow-up Lens 2/ Exit	Unscheduled Visit
Subjective rating with study lenses: output output	-	√ (Follow-up Lens 1)	√	~
AEs	✓	✓	✓	✓
Device deficiencies	✓	✓	✓	✓
Exit Form	(✓)	(✓)	(✓)	(✓)

^(✓) assessment performed as necessary, eg, decrease of VA by 2 lines or more with investigational product (IP)

^{*} Source only

[†] Comments, optional

Document: TDOC-0054657 Version: 1.0; CURRENT; Most-Recent; Effective

Status: Effective

Date/Time (mm/dd/yyyy GMT):	Signed by:	Justification:
11/16/2017 19:56:35		
11/16/2017 20:21:41		
11/16/2017 22:12:19		
11/17/2017 16:23:01
